### 5.3 Agent Administration

#### 5.3.1 Palbociclib

Palbociclib will be administered at 100 mg daily orally on Days 1-21 of each cycle for patients in Cohort A and 125 mg daily orally on Days 1-21 of each cycle for Cohort B.

Palbociclib will be provided as 125 mg, 100 mg or 75 mg pills.

Palbociclib should be taken as follows:

- Patients should be instructed to take their dose at approximately the same time each day (+/- 4-hour window acceptable around each dose). On days when ganitumab is administered, the timing of palbociclib administration can proceed independently of the timing of ganitumab administration.
- Each dose of palbociclib should be taken with water (no required minimum volume).
- Pills should be swallowed whole and not chewed, crushed or split.
- Palbociclib may be provided as a tablet or capsule formulation. Instructions differ based on formulation. Tablets may be taken with or without food. Capsules must be taken within 1 hour of eating.
- If a patient vomits or misses (not taken within 6 hours of the intended time) a dose of palbociclib, the patient should take the next dose as scheduled and not redose.
- Patients should inform the investigational site staff of any missed or delayed doses.

Each dose of palbociclib will be recorded in a medication diary. The medication diary will be returned to clinic staff at the end of each cycle. Palbociclib blister packs (tablet formulation) or pill bottles (capsule formulation) should be returned to the clinic at the start of each subsequent cycle. The study team will perform pill counts.

In the absence of safety data in pregnant animals or humans, women who are pregnant or could be pregnant should use gloves when handling palbociclib. Caregivers should use caution when cleaning up emesis, with the use of gloves recommended.

### 5.3.2 Ganitumab

Ganitumab is administered via IV on days 1 and 15 of each cycle.

Ganitumab will be administered at a dose of 18 mg/kg.

Ganitumab should be administered as follows:

- The infusion line should be thoroughly flushed with saline before and after administration of ganitumab to avoid mixing with other drug products or IV solutions.
- The first dose should be administered over 60 minutes without premedication. If well tolerated over 60 minutes, subsequent infusions may be administered over 30 minutes, at the investigator's discretion. Infusion times can be extended to a maximum of 120 minutes for subjects unable to tolerate the 60-minute infusion.
- Doses over 2100 mg should be infused over 120 minutes. If well tolerated over 120 minutes, subsequent infusions may be administered over 60 minutes at the investigator's discretion.
- The dose of ganitumab is to be based upon the participant's weight in kg obtained within 7 days of the start of each cycle. There is no adjustment for obesity.

See section 8.1.2.5 for ganitumab preparation.

### 5.3.3 Allowed Local Control Measures

Patients may undergo surgery and/or radiotherapy to sites of disease according to the following rules:

- Only after confirmed response (meaning two consecutive disease evaluation scans showing at least a partial response);
- Hold both study drugs at least 1 week prior to surgery and for a minimum of 2 weeks following surgery;
- Hold both study drugs at least 24 hours prior to radiation, during radiation, and for a minimum of 1 week following radiation;
- Defer to institutional standard for surgical or radiation approaches;
- Thoracic radiation is forbidden while on therapy given potential risk of pneumonitis in patients treated with ganitumab.

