## 5.5 General Concomitant Medication and Supportive Care Guidelines

### 5.5.1 Concomitant Medications

- 5.5.1.1 No other cancer chemotherapy or anticancer therapies are allowed except local measures specified in section 5.3.3.
- 5.5.1.2 Appropriate antibiotics, blood products, anti-emetics, fluids, electrolytes and general supportive care are to be used as necessary (see Section 5.5.2).
- 5.5.1.3 Patients may not receive corticosteroids EXCEPT under the following conditions:
  - Physiologic replacement for patients with adrenal insufficiency
  - As needed to manage allergic reactions
  - To prevent transfusion reactions
  - Inhaled or topical administration
  - In patients with metastatic CNS disease, use of doses that have been stable or tapering since enrollment.
- 5.5.1.4 Subjects must not receive any of the QT prolonging agents in Appendix B, Table 12. QT prolonging agents in Appendix B, Table 13 are to be used with caution.
- 5.5.1.5 Subjects must not receive strong CYP3A inducers or inhibitors (delineated in Appendix B, Table 10) within 7 days of enrollment and while on protocol therapy. Subjects receiving moderate CYP3A inhibitors should be monitored (see Appendix B, Table 11).

Subjects receiving concomitant medications metabolized by CYP3A enzymes should be monitored at the discretion of the investigator, particularly if the concomitant medication has a narrow therapeutic window and/or is known to rely strongly on one of these isoenzymes for its metabolism. Such medications may have an interaction with palbociclib.

Patients must avoid consumption of grapefruit products, and Seville oranges or products containing the juice of each while on protocol therapy, due to potential CYP3A4 interaction with the study medications. Orange juice is allowed.

Please refer to the palbociclib and ganitumab Investigator's Brochures for additional drug interaction information.

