### 11.1 Key Definitions

Duration of overall response: The duration of overall response is measured from the time measurement criteria are met for CR or PR (whichever is first recorded) until the first date that recurrent or progressive disease is objectively documented (taking as reference for progressive disease the smallest measurements recorded since the treatment started, or death due to any cause. Participants without events reported are censored at the last disease evaluation).

Duration of overall complete response: The duration of overall CR is measured from the time measurement criteria are first met for CR until the first date that progressive disease is objectively documented, or death due to any cause. Participants without events reported are censored at the last disease evaluation.

Duration of stable disease: Stable disease is measured from the start of the treatment until the criteria for progression are met, taking as reference the smallest measurements recorded since the treatment started, including the baseline measurements.

Progression-Free Survival: Progression-Free Survival (PFS) is defined as the time from registration to the earliest time of progression or death due to any cause. Participants alive without disease progression are censored at date of last disease evaluation.

Overall Survival: Overall Survival (OS) is defined as the time from registration to death. Participants alive are censored at date of last follow-up.

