### 11.2.3 Response Criteria

#### 11.2.3.1 Evaluation of Target Lesions

**Target lesions:** All measurable lesions up to a maximum of 2 lesions per organ and 5 lesions in total, representative of all involved organs, should be identified as **target lesions** and recorded and measured at baseline. Target lesions should

be selected on the basis of their size (lesions with the longest diameter), be representative of all involved organs, but in addition should be those that lend themselves to reproducible repeated measurements. It may be the case that, on occasion, the largest lesion does not lend itself to reproducible measurement in which circumstance the next largest lesion which can be measured reproducibly should be selected. A sum of the diameters (longest for non-nodal lesions, short axis for nodal lesions) for all target lesions will be calculated and reported as the baseline sum diameters. If lymph nodes are to be included in the sum, then only the short axis is added into the sum. The baseline sum diameters will be used as reference to further characterize any objective tumor regression in the measurable dimension of the disease.

Complete Response (CR): Disappearance of all target lesions. Any pathological lymph nodes (whether target or non-target) must have reduction in short axis to <10 mm.

Partial Response (PR): At least a 30% decrease in the sum of the diameters of target lesions, taking as reference the baseline sum diameters.

Progressive Disease (PD): At least a 20% increase in the sum of the diameters of target lesions, taking as reference the smallest sum on study (this includes the baseline sum if that is the smallest on study). In addition to the relative increase of 20%, the sum must also demonstrate an absolute increase of at least 5 mm. (Note: the appearance of one or more new lesions is also considered progressions).

Stable Disease (SD): Neither sufficient shrinkage to qualify for PR nor sufficient increase to qualify for PD, taking as reference the smallest sum diameters while on study.

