#### 11.2.3.5 Evaluation of Best Overall Response

The best overall response is the best response recorded from the start of the treatment until disease progression/recurrence (taking as reference for progressive disease the smallest measurements recorded since the treatment started). The patient's best response assignment will depend on the achievement of both measurement and confirmation criteria.

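### Best overall response stays open after permitted surgery or radiotherapy, so a resected PR can be recorded as a CR, and response durations and PFS run through local control with no separate report

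*Combined protocol and SAP*

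**What the plan says.** **Local control is part of the protocol.** Section 5.3.3 states: "Patients may undergo surgery and/or radiotherapy to sites of disease according to the following rules". Its first condition restricts this to confirmed responders: "Only after confirmed response (meaning two consecutive disease evaluation scans showing at least a partial response". The section then sets minimum drug holds before and after each procedure, so study treatment is expected to resume. Section 5.5.1.1 makes the exemption explicit: "No other cancer chemotherapy or anticancer therapies are allowed except local measures specified in section 5.3.3". Section 5.6 does not list local control among the reasons for ending protocol therapy, and note 9 of the Section 10 calendar continues restaging to Cycle 12. These patients therefore go on being assessed after the procedure.

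**Best response stays open.** Section 11.2.3.5: "The best overall response is the best response recorded from the start of the treatment until disease progression/recurrence". Section 11.2.3.1: "Complete Response (CR): Disappearance of all target lesions". Neither makes an exception for lesions removed or irradiated on study.

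**Durations and PFS run on.** Section 11.1 ends duration of response at progression or death: "until the first date that recurrent or progressive disease is objectively documented". PFS in the same section "is defined as the time from registration to the earliest time of progression or death due to any cause", and otherwise "Participants alive without disease progression are censored at date of last disease evaluation". Section 13.5 restates PFS for the Kaplan-Meier analysis. Neither section mentions local control.

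**The responder endpoint pools CR and PR.** Sections 13.1.1 and 13.3.2 classify each patient as responder or not, and a confirmed PR is enough.

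**The concern.** RECIST response is meant to show what the drugs did to measured disease. When a surgeon removes the remaining lesions, their disappearance says nothing about the drugs. With no cut-off, the plan's definitions allow that disappearance to upgrade a PR to a CR and to start a CR-duration clock.

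PFS raises a related but weaker question. Only confirmed responders can have local control, and they are the patients most likely to form the right-hand end of the curve. A reader who sees a few long PFS times cannot tell from the planned output whether they followed drug treatment alone or drug treatment plus resection or radiotherapy. In cohorts of 15 and 12, one or two such patients are visible in the results.

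**Working it through.** **1. Can a resected PR be recorded as a confirmed CR?** The plan requires:
- all target lesions gone and pathological nodes below 10 mm in short axis (11.2.3.1);
- all non-target lesions gone and tumor markers normal (11.2.3.2);
- no new lesion, and confirmation at 4 weeks or more (overall response table in 11.2.3.5).

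Complete resection of residual disease can meet every line. Restaging every two cycles supplies a second scan more than 4 weeks later. Partial local control leaves the patient at PR.

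**2. Does any other rule close the gap?**
- Section 11.2.1 treats lesions in a previously irradiated area as neither measurable nor evaluable unless they progress after radiation. It concerns measurability of irradiated sites. It does not cover resected lesions, best response, durations or PFS.
- Section 13.3.1 covers non-protocol therapy given between first PR and confirmation. Local control under 5.3.3 is protocol-allowed and comes after confirmation.
- Section 11.3 sends baseline, first-response and confirming scans for central review. It gives no rule for scans after a procedure.

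**3. Is the primary test affected?** The stated operating characteristics reproduce.
- Cohort A (n = 15, success at 4 or more): P(success) = 1 − Σ(x = 0 to 3) C(15,x) pˣ(1−p)^(15−x). At p = 0.10 this is 0.0556 (stated 0.056). At p = 0.40 it is 0.9095 (stated 91%).
- Cohort B (7 then 5, stop at 0 of 7, success at 2 or more of 12): P(success) = 1 − (1−p)^7 − 7p(1−p)^11. At p = 0.04: 1 − 0.7514 − 0.1787 = 0.0698 (stated 0.07). At p = 0.32: 1 − 0.0672 − 0.0322 = 0.9006 (stated 90%).

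A patient must already be a confirmed responder before local control, and an upgrade from PR to CR leaves the pooled count the same. These figures do not move, with or without the fix.

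**4. How many patients could have local control?** Expected responders are n × p.
- Cohort A: 15 × 0.10 = 1.5, up to 15 × 0.40 = 6.
- Cohort B: 12 × 0.04 = 0.48, up to 12 × 0.32 = 3.84, ignoring the stage 1 stop.

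How many of these would have local control is not stated.

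**5. Upper bound per patient.** Take the planned evaluable number as denominator and assume no censoring before the time point. One patient is then 1/15 = 6.7 points in Cohort A and 1/12 = 8.3 points in Cohort B. Two are 13.3 and 16.7 points.

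**6. Illustration of likely size (all inputs assumed).** Non-responders have median PFS of 2 months. Responders respond at month 2, are event-free to month 3, and then have a residual median of 5 months. Local control halves the residual hazard, giving a residual median of 10 months, and every responder has it. With response rate r, 12-month PFS is (1−r)·2^(−12/2) + r·2^(−9/5) without local control. With it, the last term becomes r·2^(−9/10). The powers are 0.0156, 0.2872 and 0.5359.

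| r | Without | With |
|---|---|---|
| 10% | 0.9×0.0156 + 0.1×0.2872 = 4.3% | 0.9×0.0156 + 0.1×0.5359 = 6.8% |
| 27% | 0.73×0.0156 + 0.27×0.2872 = 8.9% | 0.73×0.0156 + 0.27×0.5359 = 15.6% |
| 40% | 0.6×0.0156 + 0.4×0.2872 = 12.4% | 0.6×0.0156 + 0.4×0.5359 = 22.4% |

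Median duration of response goes from 3 + 5 − 2 = 6 months to 3 + 10 − 2 = 11 months. Median PFS hardly moves: at r = 40% it goes from 3.98 to 4.31 months, about 0.3 months. The effect is on response duration and the tail of PFS, not the PFS median.

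**The case against.** The strongest reply has four parts.

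- **Little of this is a planned analysis.** Section 13 plans no CR-rate, response-duration or landmark-PFS analysis. Section 13.5 covers PFS and OS only, descriptively and with no comparator. This stands, and it limits the weight of the point. Section 11 still defines best response and the durations, so they can be reported under those rules.
- **Following PFS through local control is legitimate.** The protocol permits local control, so this is a treatment-policy estimand. The secondary objective in 1.3.1 describes the patients as treated with the combination, which does not promise a drug-only effect. A reader might infer that the planned PFS is wrong; the documents do not support that. Censoring at local control would also be informative, because only confirmed responders can have it. Both parts stand, so the censored curve can only be supportive.
- **CR is not automatic.** A reader might infer that any resected PR becomes a CR. Step 1 shows that all disease must be gone and the finding confirmed. Thoracic radiation is also forbidden on therapy, which narrows use further.
- **The percentage points are ceilings.** A full 1/15 or 1/12 shift in PFS needs a patient who would have progressed before the time point and did not because of local control. The two-patient figures need two of them. In Cohort B, two responders already meet the success threshold, which has probability about 0.07 under the null.

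None of this supplies the missing cut-off for best response, and no section reports the affected patients separately.

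**Conclusion.** The point holds in a limited form. As written, the plan can record a surgically produced CR, and the CR duration that follows, as response to the drugs. It also gives no means of seeing how far PFS depends on local control.

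A reader might go further and infer that the efficacy conclusion is biased. It is not: the CR-plus-PR count, the Cohort A threshold and the Cohort B two-stage rule are untouched.

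What is affected is the CR/PR split, the response durations and mainly the tail of the descriptive PFS curve. Each patient given local control contributes at most 6.7 points in Cohort A or 8.3 points in Cohort B, on the planned denominators and with no earlier censoring. The number of such patients is unknown. The illustrated shifts rest wholly on assumed hazards and full uptake. This is an inexpensive improvement worth making.

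**What to change.** - **Section 11.2.3.5:** state that best overall response (CR versus PR) is taken from assessments up to and including the last one before the first local-control procedure.
- **Section 13.5:** keep PFS followed through local control as the main analysis. Add one sensitivity Kaplan-Meier curve per cohort, censored at the date of first local control, and do the same for response duration if it is reported. Label these supportive.
- **Reporting:** give the number of patients in each cohort who had local control.
- **Data capture:** record procedure date, site and type. Section 12.1.2 lists no form specific to local therapy, so check that existing forms hold these items.
- **In the same edit:** reconcile the two PFS definitions, since the sensitivity curve needs one base. Section 11.1 counts death from any cause and censors at last disease evaluation. Section 13.5 counts death due to disease and censors at last follow-up.

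The cost is a few sentences, one extra curve per cohort and some added data capture. The CR count may be lower, and the sensitivity estimate will be less precise and informatively censored. No change to the local-control rules in 5.3.3 is proposed.

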## 5.4 Dose-Limiting Toxicity (DLT)

### 5.4.1 Definition of Dose-Limiting Toxicity

Toxicity will be graded using the CTCAE criteria, version 5. The CTCAE provides descriptive terminology and a grading scale for each adverse event listed. A copy of the CTCAE can be downloaded from the CTEP home page (<http://ctep.cancer.gov>). Any dose-limiting toxicity should be reported immediately via email to the overall Principal Investigator and to the Study Coordinator.

#### Definition of Dose-Limiting Toxicity

DLT is defined as any of the following events that are possibly, probably or definitely attributable to palbociclib or ganitumab. A DLT may occur in any cycle and will guide dose modifications, but only DLTs occurring in the first cycle will be used for implementation of the safety monitoring rule (Section 13.4).

#### *Non-Hematological DLT:*

- Any Grade 3 or higher non-hematological toxicity attributable to palbociclib or ganitumab with the specific exclusion of:
  - Grade 3 nausea and vomiting, anorexia, diarrhea or dehydration resolving to  $\leq$  grade 2 within 72 hours (note that grade 3 diarrhea requiring hospitalization would constitute DLT).
  - Grade 3 AST or ALT liver enzyme elevation that return to  $<$  grade 2 within 7 days (except as below if bilirubin also elevated). If grade 3 liver enzyme elevation occurs, palbociclib and ganitumab should be held and liver enzymes rechecked within 4 days of initial date of grade 3 abnormality to determine if DLT criteria have been met. See also Section 6.4.

**Recall:** For the purposes of this study the ULN for ALT is defined as 45 U/L and for AST is 30 U/L.

- Grade 3 hypophosphatemia, hypokalemia, hypocalcemia or hypomagnesemia responsive to oral supplementation within 72 hours.
- Grade 2 elevation of AST and/or ALT WITH total bilirubin  $> 2 \times$  ULN, in the absence of cholestasis.
- Any Grade 2 non-hematological toxicity that persists for  $\geq 7$  days and is considered sufficiently medically significant or sufficiently intolerable by patients that it requires treatment interruption.
- Any non-hematologic toxicity that results in delay in start of subsequent cycle by  $> 14$  days.

*Hematological DLT:*

- Hematological dose limiting toxicity is defined as:
  - Grade 4 thrombocytopenia or grade 4 neutropenia of any duration, in the absence of bone marrow disease; or
  - Grade 3 or higher febrile neutropenia with or without documentation of infection; or
  - Grade 3 thrombocytopenia in association with a grade 2 or higher bleeding episode; or
  - Delay in the start of subsequent cycle by  $> 14$  days due to thrombocytopenia or neutropenia, in patients without known bone marrow disease.

Patients with bone marrow metastatic disease at study entry will not be evaluable for hematologic DLT for the purposes of evaluating the toxicity monitoring rule. Such patients will follow the dose modification criteria in Section 6.2.1 in the setting of defined hematologic DLT.

Any Grade 5 toxicity that is possibly, probably, or definitely attributable to palbociclib or ganitumab will be considered a DLT.

Management and dose modifications associated with the above adverse events are outlined in Section 6.

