3.1.7 Participants must have normal organ function as defined below.

3.1.7.1 Hematologic Requirements for Subjects without Known Bone Marrow Involvement by Disease:

- Absolute neutrophil count       $>1000 / \mu\text{L}$
- Hemoglobin       $\geq 8 \text{ g/dL}$  (transfusion allowed)
- Platelets       $\geq 100,000 / \mu\text{L}$  and transfusion independent, defined as not receiving a platelet transfusion for at least 7 days prior to CBC documenting eligibility.

3.1.7.2 Hematologic Requirements for Subjects with Bone Marrow Involvement by Disease as Demonstrated on Clinically-Indicated Bone Marrow Biopsy:

- Absolute neutrophil count       $>750 / \mu\text{L}$
- Hemoglobin       $\geq 8 \text{ g/dL}$  (transfusion allowed)
- Platelets       $\geq 50,000 / \mu\text{L}$  and transfusion independent, defined as not receiving a platelet transfusion for at least 7 days prior to CBC documenting eligibility.

- Not known to be refractory to platelet or red cell transfusions.

3.1.7.3 Hepatic Function:

- Total bilirubin       $\leq 1.5 \times$  upper limit of normal for age  
Patients with Gilbert's syndrome with a total bilirubin  $< 2 \times$  upper limit of normal for age and

• ALT (SGPT)	a direct bilirubin within normal limits are permitted. $\leq 135$ U/L For the purpose of this study, the ULN for ALT is 45 U/L
• AST	$\leq 90$ U/L For the purpose of this study, the ULN for AST is 30 U/L
• Serum albumin	$\geq 2$ g/dL

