### **13.4 Interim Toxicity Monitoring Plan**

The primary endpoint for the interim toxicity monitoring rule of the study will be the occurrence of a Cycle 1 DLT that is attributable to palbociclib or ganitumab or the combination, as defined in Section 5.4.1. To be evaluable for the interim toxicity monitoring rule of Cycle 1 DLTs, a patient must receive at least one dose of either drug and have been followed for at least 30 days following the last dose of protocol therapy or to the start of Cycle 2, whichever occurs first. Additionally, any patient with Cycle 1 DLT will be considered evaluable for the interim toxicity monitoring rule. Cohorts A and B will have separate toxicity monitoring rules as the rate of DLTs is expected to differ by cohort due to differences in frontline therapy for patients in each cohort.

Toxicity as graded by CTCAE v5.0 will be recorded and monitored throughout all cycles of therapy. The number and proportion of toxicities will be tabulated by type, grade, and attribution. A given toxicity will be counted only once in a given patient, at the highest grade observed.

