#### **13.4.1 Cohort A toxicity monitoring plan**

For Cohort A, the original two-stage toxicity monitoring rule was triggered with 2 DLTs out of the first 3 evaluable patients. A new one-stage design has been developed for the remaining 12 patients, all of whom will be treated at a lower dose level than the first 3 patients (contingency A, see Section 5.4.2).

Enroll up to 12 toxicity evaluable patients. If at any time 3 or more patients have a first cycle DLT, enrollment will be paused, the trial will be reviewed by the study committee and the DSMC, and a lower dose level will be considered as outlined in Section 5.4.2. If fewer than 3 of 12 patients have a first cycle DLT, the dose level will be considered sufficiently safe for further study. This rule has the following operating characteristics. The null hypothesis is that the proportion of patients with a Cycle 1 DLT is  $\geq 39\%$  versus the alternative that the proportion with a Cycle 1 DLT is  $\leq 9\%$ . The power is 91.3% and the type 1 error is 9.5%.

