#### **13.4.2 Cohort B toxicity monitoring plan**

For Cohort B, we will utilize the following one-stage toxicity monitoring rule:

Enroll up to 12 toxicity evaluable patients. If at any time 3 or more patients have a first cycle DLT, enrollment will be paused, the trial will be reviewed by the study committee and the DSMC, and a lower dose level will be considered as outlined in Section 5.4.2. If fewer than 3 of 12 patients have a first cycle DLT, the dose level will be considered sufficiently safe for further study. This rule has the following operating characteristics. The null hypothesis is that the

proportion of patients with a Cycle 1 DLT is  $\geq 39\%$  versus the alternative that the proportion with a Cycle 1 DLT is  $\leq 9\%$ . The power is 91.3% and the type 1 error is 9.5%.

The number and proportion of toxicities will be tabulated within each cohort, by type, grade, and attribution. A given toxicity will be counted only once in a given patient, at the highest grade observed.

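### Section 13.4 lets a patient with bone marrow involvement fill one of the 12 toxicity places although 5.4.1 keeps that patient's hematologic DLTs out of the rule, so the 9.5% error is secured only if there is no such patient

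*Combined protocol and SAP*

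**What the plan says.** Eligibility section 3.1.7.2, headed "Hematologic Requirements for Subjects with Bone Marrow Involvement by Disease as Demonstrated on Clinically-Indicated Bone Marrow Biopsy", sets separate and lower entry limits for neutrophils and platelets in these patients. The provision is not confined to one cohort.

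Section 5.4.1 states that patients with marrow metastases at study entry "will not be evaluable for hematologic DLT for the purposes of evaluating the toxicity monitoring rule". Their non-hematologic DLTs and attributable grade 5 events remain DLTs.

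Section 13.4 defines who is evaluable for the rule: "a patient must receive at least one dose of either drug" and be followed to the start of Cycle 2 or for 30 days after the last dose, whichever comes first. A patient with a Cycle 1 DLT is evaluable in any case. Marrow involvement is not mentioned.

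Section 13.4.1 (Cohort A) sets the rule: "Enroll up to 12 toxicity evaluable patients. If at any time 3 or more patients have a first cycle DLT, enrollment will be paused". Section 13.4.2 (Cohort B) repeats it and adds the conclusion that follows otherwise, as 13.4.1 also does: "If fewer than 3 of 12 patients have a first cycle DLT, the dose level will be considered sufficiently safe". Both give a null DLT rate of 39% or more, an alternative of 9% or less, power of 91.3% and type 1 error of 9.5%.

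Section 13.2 replaces patients who are ineligible or not evaluable for response. It says nothing about patients who cannot be assessed for hematologic DLT.

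**The concern.** The rule counts DLTs over a fixed denominator of 12. A marrow-involved patient who completes Cycle 1 meets the evaluability definition in 13.4 and adds one to that denominator, but can add to the numerator only through a non-hematologic or grade 5 event. Everything on the hematologic list in 5.4.1 is lost for the rule in that patient, including febrile neutropenia and thrombocytopenia with bleeding.

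This affects patients who are fully treated and followed, so it is distinct from early dropout in Cycle 1. It also works in one direction: fewer events can be seen, so a dose passes more easily.

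Hematologic toxicity matters in this trial. Section 2.2.2.2 lists neutropenia and infection as the most common grade 3 events with palbociclib. Sections 2.2.2.2 and 2.6 use expected differences in hematologic toxicity to justify the different starting doses, and 2.6 uses the differing prior therapy to justify separate rules. Cohort A has already triggered its first rule, with 2 DLTs in 3 patients. What is at stake is how often a dose with an unacceptable DLT rate is labelled sufficiently safe.

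**Working it through.** **Inputs from the documents.** n = 12; pause at 3 or more Cycle 1 DLTs; null rate 39%; alternative 9% (13.4.1, 13.4.2). Response test in Cohort A: n = 15, cutoff 4 responses, null 10% (13.3.2). Maximum enrolment 33 (13.2).

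**Assumptions, not in the documents.** m = number of marrow-involved patients among the 12. h = share of DLT risk that is hematologic and so uncountable in them. The 39% is taken as the rate in fully assessable patients, so a marrow-involved patient has a countable rate q = 0.39 × (1 − h).

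**Step 1: reproduce the stated figures.**
- Type 1 error = P(X ≤ 2), X ~ Bin(12, 0.39) = 0.00265 + 0.02036 + 0.07161 = 0.0946, stated as 9.5%.
- Power = P(X ≤ 2), X ~ Bin(12, 0.09) = 0.32248 + 0.38272 + 0.20818 = 0.9134, stated as 91.3%.

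Stopping at any time on the third DLT is the same event as three or more in 12, so it changes nothing. Both figures give all 12 patients the full DLT probability.

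**Step 2: one marrow-involved patient (m = 1).** For Bin(11, 0.39), P(X ≤ 2) = 0.1328 and P(X = 2) = 0.0978. The dose passes unless the 11 give exactly two DLTs and the twelfth patient adds a third:

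P(pass) = 0.1328 − 0.0978 × q

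**Step 3: two such patients (m = 2).** For Bin(10, 0.39), P(0) = 0.00713, P(1) = 0.04561 and P(2) = 0.13121:

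P(pass) = 0.00713 + 0.04561 × (1 − q²) + 0.13121 × (1 − q)²

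| h | q | m = 0 | m = 1 | m = 2 |
|---|---|---|---|---|
| 0.25 | 0.2925 | 9.5% | 10.4% | 11.5% |
| 0.50 | 0.195 | 9.5% | 11.4% | 13.6% |
| 0.75 | 0.0975 | 9.5% | 12.3% | 15.9% |
| 1.00 | 0 | 9.5% | 13.3% | 18.4% |

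**Step 4: the other side of the rule.** With m = 2 and the same share h applied to the 9% rate, power rises from 91.3% to 93.0% (h = 0.5) or 94.6% (h = 1). The cost therefore falls on the safety error.

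**Step 5: error when only fully assessable patients are counted.** P(X ≤ 2 | 39%) = 9.5% for n = 12, 13.3% for n = 11 and 18.4% for n = 10.

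**Step 6: what refilling places would do to the Cohort A response test.** The 3 patients treated before the dose change plus the 12 under the new rule make up the planned 15. With the cutoff of 4 responses and a true rate of 10%, P(X ≥ 4) = 5.6% at n = 15 (the plan's 0.056), 6.8% at n = 16 and 8.3% at n = 17.

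**The case against.** A reader might infer that the 9.5% is simply wrong, or that the plan states that marrow-involved patients occupy places among the 12. The documents support neither.

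- **Place-taking is inferred.** It follows from the evaluability definition in 13.4; no sentence says it outright. Section 13.4 takes its DLT definition from 5.4.1, so the sponsor may have meant the 5.4.1 sentence to remove these patients from the count. But 5.4.1 withdraws them for hematologic DLT only, and 13.4 states no exception. The two sections need reconciling.
- **The 39% could be read differently.** If it means the rate of countable DLTs averaged over whatever mix is enrolled, 9.5% holds approximately. Parts of the DLT definition are themselves limited to patients without marrow disease, which lends this some support. Section 13.4.1 does not define the 39% that way.
- **The effect may be nil.** With no marrow-involved patient among the 12, the error is exactly as stated. With one such patient and a 25% hematologic share it is 10.4%. The documents give neither quantity, although separate entry limits, cycle-start criteria (5.2.2) and a dose-modification table (Table 9) show that such patients are provided for.
- **Not every hematologic event is lost, and other safeguards remain.** Grade 3 neutropenia without fever or a long cycle delay is not a DLT in anyone. Attributable non-hematologic events of grade 3 or higher, outside the listed exceptions, still count in marrow-involved patients. Toxic deaths trigger review, and the DSMC sees all toxicity.

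Excluding hematologic DLTs in marrow disease is a deliberate and understandable choice. What stands is that the denominator was not adjusted to match it.

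**Conclusion.** The point holds in conditional form. As written, 13.4 counts a marrow-involved patient among the 12 while 5.4.1 keeps that patient's hematologic DLTs out of the rule. Taking 39% as the DLT rate in fully assessable patients, and with some of that risk hematologic, the 9.5% error holds only if none of the 12 has marrow involvement. Otherwise the chance of declaring a dose with a 39% DLT rate sufficiently safe could be about 10.4–13.3% with one such patient and 11.5–18.4% with two, for a hematologic share of 25–100%. Both the number and the share are assumptions, so this is a range of possible understatement and not a demonstrated error in the stated figure. The gap is in the text for both cohorts; nothing in the documents shows how often it would arise in either.

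**What to change.** In 13.4, state that a patient with marrow involvement at entry does not count toward the 12 toxicity-evaluable patients unless he or she has a countable Cycle 1 DLT (non-hematologic or grade 5), which counts toward the three. This brings 13.4 into line with 5.4.1 and fits the existing provision that a patient with a Cycle 1 DLT is always evaluable.

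Do not require enrolment beyond the response sample size to refill the places. If fewer than 12 fully assessable patients are obtained, report the error for that number in place of 9.5%: 13.3% for 11 and 18.4% for 10. Both are slightly lower if marrow-involved patients' countable DLTs are included, since those can only add to the total.

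The cost is two sentences and a somewhat less favourable stated error. The maximum of 33 leaves 33 − 15 − 12 = 6 places above the response targets, but 13.2 intends these for inevaluable patients of all kinds. If any are used here, fix in advance which 15 Cohort A patients enter the response test, or restate its type 1 error (6.8% at 16 patients, 8.3% at 17, with the cutoff kept at 4). Refilling also would not return exactly 9.5% and 91.3% if marrow-involved patients' DLTs are counted on top of 12 full patients: with two such patients and half of the DLT risk hematologic, the error is 6.9% and the power 89.4%. No dose, DLT criterion or clinical rule needs to change.
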